| 
For the dose levels of 0.2 to 1.6 µg/day single patient cohorts are entered. The following dose cohorts will be tested within the above-mentioned dose range:
 
 • 0.2, 0.4, 0.8 and 1.6 µg/day • The DLT observation period for the single patient cohorts will be 2 weeks. If a patient has been on treatment in one of the above-mentioned dose cohorts for 2 weeks without DLT or other relevant safety findings the first patient of the next higher dose cohort will be entered if agreed on by the safety committee. If a patient has reached DLT, then the safety committee recommends 3 + 3 cohorts. Patients may not proceed to the next higher dose level before completion of 6 patients. 
One intra-patient dose escalation is allowed within the single patient dose cohorts if the initial dose is tolerated and no DLT occurs during 1st cycle. In case of DLT additional patients will be entered into this cohort following a 3 + 3 design.
 
For the dose levels ≥ 3.2 µg/day 3-6 patients will be treated per dose level and observed for 4 weeks during the first cycle before decision for dose escalation to the next dose cohort is made.
 
The following dose cohorts will be tested within the above-mentioned dose range:
 
3.2, 6.5, 13, 25, 50, 100, 200, 400 and 800 µg/day.. Intermediate dose cohorts with 50% increments of previous dose will be entered if determined by the safety committee. Increments to the next higher dose will not exceed 2-fold increases.
 
The DLT observation period will be extended to 4 weeks for all future cohorts before decision for dose escalation within the next dose cohort is made:
 
 • Per dose level 1 patient will be enrolled and treated for 1 week before all remaining patients for this cohort can be entered. Additional patients should not start treatment before the previous patient has been treated for 48 hours in order to monitor initial transient toxicities due to cytokine release syndrome. • Once the MTD of BI 836909 is determined up to 6 additional patients will be treated at the MTD or the recommended dose for confirmation of safety. | | | |

Proprietary confidential information.

© 2018 Boehringer Ingelheim International GmbH or one or more of its affiliated companies. All rights reserved.

This document may not - in full or in part - be passed on, reproduced, published or otherwise used without prior written permission.

| | | | |

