For the dose levels 0.2 to 1.6 µg/day single patient cohorts are entered since no clinical activity is expected at these doses.

If a patient has been on treatment in one of the above-mentioned dose cohorts for 2 weeks without DLT the first patient of the next higher dose cohort will be entered if agreed on by the safety committee. If a patient has reached DLT, then the safety committee recommends the switch to a 3 + 3 cohort for the dose level at which the DLT occurred. Patients may not proceed to the next higher dose level before completion of 6 patients.

One intra-patient dose escalation is allowed within the single patient dose cohorts if the initial dose is tolerated well and no DLT occurs during 1st cycle. In case of DLT additional patients will be entered into this cohort following a 3+3 design.

For the dose levels ≥ 3.2 µg/day 3-6 patients will be treated per dose level and observed for 4 weeks during the first cycle before decision for dose escalation to the next dose cohort is made.

Per dose level 1 patient will be enrolled and treated for 1 week, then further patients will be enrolled. Patients should be entered sequentially. Additional patients should not start treatment before the previous patient has been treated for 48 hours in order to monitor initial transient toxicities due to cytokine release syndrome.

In the dose escalation part the trial safety committee (for details see [Section 3.1.1](#)) can determine to enter additional and intermediate dose cohorts at any time e.g. if DLTs or other safety events, pharmacodynamics activity or antitumor efficacy occur. The safety committee will also determine to switch from single patient cohorts to a 3+3 design at doses below **3.2µg/d** if DLTs, pharmacodynamic activity or antitumor efficacy occur.

PK/PD data might be taken into account for dose escalation decisions if available.

Patients should be entered sequentially. Treatment initiation of more than 1 new patient per day will not be permitted during the dose escalation phase.

Once the MTD or the recommended dose for better characterization of safety and early evaluation of anti-tumour activity is determined up to 6 additional patients will be treated with MTD or the recommended dose.

Proprietary confidential information.

© 2018 Boehringer Ingelheim International GmbH or one or more of its affiliated companies. All rights reserved.

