For the dose levels $\geq 3.2 \mu\text{g/day}$ 3-6 patients (3+3 design) will be treated per dose level and observed for 4 weeks before decision for dose escalation to the next dose cohort is made.

If one patient of the cohort of three patients experiences a dose limiting toxicity (DLT) (for definition see [5.2.1.1](#)) within the first cycle (4 weeks of continuous infusion), three additional patients will be treated at the same dose level according to a standard 3+3 design.

If at least two out of up to six patients at a dose level experience a DLT, the MTD has been exceeded and the dose will be de-escalated until a dose level is reached in which at most one DLT out of six patients is observed ([R01-0028](#)).

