| Dose µg/day | Patients per cohort | Observation time of ongoing patients before enrolment/entry of next patient/cohort |
|-------------|---------------------|--|
| 0.2 | 1 | 2 weeks, then enrol next cohort |
| 0.4 | 1 | As in previous cohort |
| 0.8 | 1 | As in previous cohort |
| 1.6 | 1 | As in previous cohort |
| 3.2 | 3 (+3) | 1 week for first patient, then enter next two patients; additional patients should not start treatment before the previous patient has been treated for 48 hours in order to monitor initial transient toxicities due to cytokine release syndrome. All 3 must have completed 4 weeks before enrolling next cohort |
| 6.5 | 3 (+3) | As in previous cohort |
| 13 | 3 (+3) | As in previous cohort |
| 25 | 3 (+3) | As in previous cohort |
| 50 | 3 (+3) | As in previous cohort |
| 100 | 3 (+3) | As in previous cohort |
| 200 | 3 (+3) | As in previous cohort |
| 400 | 3 (+3) | As in previous cohort |
| 800 | 3 (+3) | As in previous cohort |

*Intermediate dose cohorts may be added based on decision of the safety committee ([see table 3.1:1](#)) and will follow the above-mentioned rules.

For details see [Section 3.1](#).

During the dose-escalation phase, each patient will receive a continuous infusion of BI 836909 given for 4 weeks followed by observation for 2 weeks after termination of the continuous

Proprietary confidential information.

© 2018 Boehringer Ingelheim International GmbH or one or more of its affiliated companies. All rights reserved.

This document may not - in full or in part - be passed on, reproduced, published or otherwise used without prior written permission.

infusion. Treatment is given until progression according to IMWG response criteria (see [Appendix 10.1](#)), non-acceptable toxicity, patient decision to withdraw consent, investigator's decision. In case of clinical benefit a maximum of 5 cycles is administered. In case of ongoing clinical benefit additional 5 treatment cycles can be given if considered indicated by the treating investigator.

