5.2.1.1 Dose limiting toxicity

Dose limiting toxicity (DLT) is defined as any drug-related non-haematological adverse event CTCAE version 4.03 grade 3 or higher. The following grade 3 events will not be considered

Proprietary confidential information.

© 2018 Boehringer Ingelheim International GmbH or one or more of its affiliated companies. All rights reserved.

This document may not - in full or in part - be passed on, reproduced, published or otherwise used without prior written permission.

DLT: febrile neutropenia and infection responding to antibiotic/anti-infective treatment within 48 hours, fatigue, headache, insomnia, fever, hypotension.

Laboratory parameters of grade ≥ 3 but not considered clinically relevant and/or responding to routine medical management, will not be considered dose limiting toxicities.

Additional events that are considered DLT include:

- Persistent grade 4 neutropenia or thrombocytopenia until day 56 in the absence of detectable Multiple Myeloma as it may reflect a marrow toxic effect of BI 836909.

If infusion related reactions (IRR) or cytokine release syndromes (CRS) \geq grade 2 occur or constitute DLT events the safety committee may decide to switch to step dosing for the respective and any higher dose cohort. In that case the infusion will be started at 10(-30)% of the target dose on day 1 of the course and will be escalated to the full target dose from day 9 of course 1 on for the remainder of the course. Patients will be hospitalized and pre-medicated for the dose increase the same way they are for start of treatment. Once the safety committee decides to switch to step dosing patients that may have developed DLT due to IRR or CRS events may be replaced at the respective cohort by additional patients who will receive treatment with the adapted administration schedule (step dosing).

Although hematological adverse events (e.g. anemia, thrombocytopenia, neutropenia, lymphopenia) will not be considered DLT, complications resulting from hematological events, e.g. bleeding due to thrombocytopenia or grade 4 infection due to neutropenia are classified as non-hematological adverse events and are covered by the above definition of DLT. Nevertheless, hematological adverse events will be considered for definition of the dose for further development.

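### The grade 4 cytopenia DLT is established only at day 56, but the escalation count is taken at 4 weeks (2 weeks in single-patient cohorts), and no rule says how an unresolved case is counted

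*Protocol*

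**What the plan says.** **The criterion.** Protocol Section 5.2.1.1 excludes haematological events from the DLT definition, apart from their non-haematological complications such as bleeding and one further item: "Persistent grade 4 neutropenia or thrombocytopenia until day 56 in the absence of detectable Multiple Myeloma". The day from which 56 is counted is not stated.

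**The decision point.**
- Synopsis, single-patient cohorts (0.2 to 1.6 µg/day): "The DLT observation period for the single patient cohorts will be 2 weeks".
- Synopsis, later cohorts: "The DLT observation period will be extended to 4 weeks for all future cohorts".
- Section 3.1, doses from 3.2 µg/day: patients are "observed for 4 weeks during the first cycle before decision for dose escalation to the next dose cohort is made".
- Table 4.1.4:1: "All 3 must have completed 4 weeks before enrolling next cohort".
- Section 3.2 expands a cohort when one of three patients has a DLT "within the first cycle (4 weeks of continuous infusion), three additional patients will be treated at the same dose level". It adds: "If at least two out of up to six patients at a dose level experience a DLT, the MTD has been exceeded".

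**The MTD and its analysis.** Section 5.2.1 bases the MTD on cycle 1 DLTs. Later DLT-type events are considered when confirming it, but only for patients who receive more than one cycle. Section 4.1.4.5 replaces patients who stop permanently for a reason other than DLT. SAP Section 6.3 takes the primary DLT analysis from the MTD evaluation set, which leaves out replaced patients. SAP Section 7.8.1 closes Course 1 at the start of cycle 2 or 30 days after the last cycle 1 dose, whichever is earlier, and also tabulates DLTs over all courses.

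**The concern.** One component of the primary endpoint has a time point twice as long as the period after which the 3+3 count is taken. A patient with grade 4 neutropenia or thrombocytopenia ongoing at the review is neither a DLT nor clear of one. The written definition has only two states, so this patient falls on the DLT-free side. A level that might later read 1/3 or 2/3 can read 0/3 or 1/3 when the committee meets, with the next step about 2-fold higher. In the text available, no rule says how the patient is counted at the review, or what follows if the DLT is confirmed after the next level has opened.

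**Working it through.** The plan gives no DLT rate or operating characteristic, so there is no figure to reproduce. The check is calendar arithmetic on the protocol's own windows. Day 1 is assumed to be the first infusion day of course 1, so study day = elapsed days + 1.

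**1. Three-patient cohort, fastest entry.** Section 3.1 and Table 4.1.4:1 require 1 week after the first patient and 48 hours between later ones.
- Starts, in elapsed days: 0, 7, 7 + 2 = 9.
- Decision when the third completes 4 weeks: 9 + 28 = 37.
- Follow-up: 37 − 0 = 37, 37 − 7 = 30, 37 − 9 = 28 days, which are study days 38, 31 and 29.
- Short of day 56 by 18, 25 and 27 days.
- The next cohort can start on elapsed days 37, 44 and 46. The third lower-dose patient reaches day 56 on elapsed day 9 + 55 = 64. All three patients of the next cohort can be on the higher dose before then.

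**2. Slower entry.** The earlier patients gain follow-up. The last patient's 28 days trigger the decision, so that patient is always at about study day 29.

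**3. Expanded cohort.** If patients 4 to 6 start at the first decision (elapsed days 37, 39, 41), the six-patient decision falls on day 41 + 28 = 69. Their study days are then 33, 31 and 29. Only the first three have passed day 56.

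**4. Single-patient cohorts.** At 2-week steps the starts are study days 1, 15, 29 and 43. Three higher doses can open before the first patient reaches day 56.

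**5. End of cycle 1.** A 6-week cycle ends on day 42, before day 56. The SAP's Course 1 window behaves differently:
- Cycle 2 on schedule (day 43): the window closes before day 56.
- Cycle 2 not started: 28 + 30 = about day 58. Day 56 is inside if the last cycle 1 dose was on day 56 − 30 = 26 or later.
- Example: infusion stopped on day 20 for cytopenia and not resumed. Course 1 closes on day 20 + 30 = 50, before day 56.

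The SAP does not say whether this DLT is dated by onset or by confirmation. Dating by onset would place a case that began in cycle 1 inside Course 1.

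**6. Provisions that might catch the case later.** Section 4.1.4.2 requires recovery to grade 1 or the pre-treatment value before a new cycle, and Section 4.1.4.4 ends treatment after a delay of more than 2 weeks (42 + 14 = day 56). A patient meeting the criterion would normally not have started cycle 2, so the Section 5.2.1 provision for patients with more than one cycle would not apply. The patient in the example passes the 14-day limit at about day 20 + 14 = 34 and stops without a DLT. Read literally, Section 4.1.4.5 then replaces that patient, who leaves the MTD evaluation set.

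**7. Illustrative size.** Let q be the rate of this DLT (assumed; not in the documents) and k the number of patients in a cohort of three still short of day 56. The chance that at least one unresolved case later becomes a DLT is 1 − (1 − q)^k. Here k = 3 at the fastest entry and k = 1 at the slowest.

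| q (assumed) | k = 3 | k = 1 |
|---|---|---|
| 2% | 1 − 0.98³ = 5.9% | 2% |
| 5% | 1 − 0.95³ = 14.3% | 5% |
| 10% | 1 − 0.90³ = 27.1% | 10% |

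**The case against.** The case on the other side has real weight.

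- **Release is not automatic.** Section 3.1.1 requires a safety meeting before each escalation, on all available data, and Section 3.1 lets the committee add cohorts at any time. Safety laboratories are done at every visit, so an ongoing grade 4 cytopenia would be seen. This stands: the next dose may open; it does not open by itself. But the committee's power is discretionary, and the counting rule it applies has no pending state.
- **The final MTD has later checks.** DLTs over all courses are tabulated, haematological events inform the dose for further development (Section 5.2.1.1), and the two-in-six rule carries no time limit of its own. Since such a patient should not start cycle 2, the Course 1 window usually runs to about day 58. This stands in part. It fails when the last cycle 1 dose was before day 26 and the event is dated by confirmation, or when the patient has been replaced.
- **Complications count at once.** Bleeding or grade 4 infection from cytopenia is already a DLT without waiting for day 56. This stands.
- **The event is probably uncommon.** The criterion also requires no detectable myeloma. This stands and limits the size.
- **The text is incomplete.** The body of Section 7.4 and some text at the end of Section 3.1 are not in the public version, so the absence of a rule cannot be fully verified.

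**Conclusion.** The mismatch is firm for the escalation decision. At 4 weeks, or 2 weeks in the single-patient cohorts, the last patient of a cohort can never have met the day-56 criterion, and at the fastest entry none can. By the written definition, such a patient counts as DLT-free at the review.

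For the final MTD the fault is weaker but not closed, because the provision for later events, the replacement rule and the Course 1 window can each leave out the kind of patient the criterion describes.

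A reader might infer that the MTD is biased upward. The documents do not support that. The omission at the review can only lower the count, but the committee may hold or expand a level, later DLTs are tabulated, and the event rate is unknown. The percentages in the table rest on assumed rates and ignore any committee action; they are not estimates for this trial. The practical size is probably small. The point still merits correction because it concerns a primary-endpoint component in a first-in-human trial. It assumes that day 56 is counted from the first infusion day of course 1.

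**What to change.** Reconcile protocol Section 5.2.1.1 with the synopsis, Sections 3.1, 3.2, 4.1.4.5 and 5.2.1 and Table 4.1.4:1, and with SAP Sections 6.3, 7.4 and 7.8.1. In the counting rule and the SAP:

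1. Record a patient with grade 4 neutropenia or thrombocytopenia unresolved at the review as DLT pending, not as DLT-free.
2. Do not treat that patient as replaceable for a non-DLT reason while pending.
3. Re-take the count for that dose level at day 56 or at recovery.
4. Attribute a confirmed case to cycle 1 at the assigned dose in the MTD evaluation set analysis.
5. State the origin of day 56.

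Whether escalation proceeds while a case is pending, and how a level already opened is handled, is for the sponsor and safety committee to decide and write down.

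**Cost.** A few sentences and no extra patients. The final count for a level may wait up to about 4 weeks in the uncommon pending case. Weekly safety laboratory visits already apply when a course is delayed for an adverse event (Section 5.2.4.1), but they do not cover myeloma detection. M-protein is scheduled on days 1 and 29 of each cycle and at EOT. Marrow is scheduled at baseline, when M-protein or free light chains become undetectable, on day 29 of cycle 3 and at EOT (Section 5.1.2.1). The assessment of undetectable myeloma near day 56 must be matched to that schedule.

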5.2.2 Assessment of adverse events

5.2.2.1 Definitions of adverse events

Adverse event

An adverse event (AE) is defined as any untoward medical occurrence in a patient or clinical investigation subject administered a pharmaceutical product and which does not necessarily have a causal relationship with this treatment.

An AE can therefore be any unfavourable and unintended sign (including an abnormal laboratory finding) symptom, or disease temporally associated with the use of a medicinal product, whether or not considered related to the medicinal product.

Serious adverse event

A serious adverse event (SAE) is defined as any AE which:

- results in death,
- is life-threatening,
- requires inpatient hospitalization or prolongation of existing hospitalization,

Proprietary confidential information.

© 2018 Boehringer Ingelheim International GmbH or one or more of its affiliated companies. All rights reserved.

This document may not - in full or in part - be passed on, reproduced, published or otherwise used without prior written permission.

- results in persistent or significant disability or incapacity,
- is a congenital anomaly/birth defect,

or

- is to be deemed serious of any other reason it is an important medical event when based upon appropriate medical judgement which may jeopardize the patient and may require medical or surgical intervention to prevent one of the other outcomes listed in the above definitions.

Life-threatening in this context refer to an event in which the patient was at risk of death at the time of the event; it does not refer to an event that hypothetically might have caused death if more severe.

AEs considered “Always Serious”

In accordance with the European Medicines Agency initiative on Important Medical Events, Boehringer Ingelheim has setup a list of AEs, which by their nature, can always be considered to be “serious” even though they may not have met the criteria of an SAE as given above.

The latest list of “Always Serious AEs” can be found in the RDC system. These events should always be reported as SAEs as described in [Section 5.2.3](#).

Adverse Events of special interest (AESIs)

The term AESI relates to any specific AE that has been identified at the project level as being of particular concern for prospective safety monitoring and safety assessment within this trial, e.g. the potential for AEs based on knowledge from other compounds in the same class. AESI need to be reported to the Sponsor’s Pharmacovigilance Department within the same timeframe that applies to SAE, see [Section 5.2.3](#).

The following are considered AESIs:

- Infusion-related reactions and cytokine release syndromes (CTCAE version 4.03 grade 3 or higher)
- Tumour lysis syndrome
- CNS adverse events grade 2 or higher
- Any event that qualifies for DLT (refer to [Section 5.2.1.1](#))
- Hepatic Injury

A hepatic injury is defined by the following alterations of hepatic laboratory parameters ([Appendix 10.6](#)):

- an elevation of AST and/or ALT ≥ 5 fold ULN combined with an elevation of total bilirubin ≥ 2 fold ULN (if ratio of conjugated/total bilirubin is > 0.5) measured in the same blood draw sample, and/or
- Marked peak aminotransferase (ALT, and/or AST) elevations ≥ 10 fold ULN

Proprietary confidential information.

© 2018 Boehringer Ingelheim International GmbH or one or more of its affiliated companies. All rights reserved.

This document may not - in full or in part - be passed on, reproduced, published or otherwise used without prior written permission.

These lab findings constitute a hepatic injury alert and the patients showing these lab abnormalities need to be followed up according to the “DILI checklist” provided via the RDC-system. In case of clinical symptoms of hepatic injury (icterus, unexplained encephalopathy, unexplained coagulopathy, right upper quadrant abdominal pain, etc.) without lab results (ALT, AST, total bilirubin) available, the investigator should make sure these parameters are analysed, if necessary in an unscheduled blood test. Should the results meet the criteria of hepatic injury alert, the procedures described in the DILI checklist should be followed.

Work-up as outlined in the “DILI-checklist” will serve to confirm the initial abnormality, obtain a comprehensive history and medical assessment, assess the severity of liver injury, evaluate data for potential alternative causes and decide on management of trial drug. When performing all of the required examinations, the investigator is encouraged to use clinical judgement, based on the patient’s disease, comorbidities, clinical situation, past viral infections and risk for reactivation, exposure, prior therapy for malignant disease, co-medications and other factors as applicable. The sequence of tests in the DILI checklist may be used as guidance. The findings from the hepatic imaging (including comparison to prior imaging if available) must be made available as soon as possible as part of the adverse event reporting process and/or on the respective CRF pages. In the event the aetiology of the abnormal liver test results is not identified based on the imaging (e.g. biliary tract, pancreatic or intrahepatic pathology), the “DILI checklist” must be completed. Virus reactivation should be assessed by viral load and PCR testing where possible. Diagnostics for auto-immune hepatitis, Wilson’s disease and haemochromatosis can be completed at the end of all assessments, as these examinations will not change within a short time period but can be considered proof of a long persisting chronic condition. In case a laboratory parameter of the DILI checklist cannot be performed, the investigator should provide a comment including a brief assessment of the relevance of this parameter for the overall evaluation of DILI.

Intensity of adverse event

The intensity of the AE should be judged based on the following:

- Mild: Awareness of sign(s) or symptom(s) which is/are easily tolerated
- Moderate: Enough discomfort to cause interference with usual activity
- Severe: Incapacitating or causing inability to work or to perform usual activities

The intensity of adverse events should be classified and recorded according to the Common Terminology Criteria for Adverse Events (CTCAE) version 4.03 in the (e)CRF.

Causal relationship of adverse events

Medical judgment should be used to determine the relationship, considering all relevant factors, including pattern of reaction, temporal relationship, de-challenge or re-challenge, confounding factors such as concomitant medication, concomitant diseases and relevant history.

- Yes: There is a reasonable causal relationship between the investigational product administered and the AE.

Proprietary confidential information.

© 2018 Boehringer Ingelheim International GmbH or one or more of its affiliated companies. All rights reserved.

This document may not - in full or in part - be passed on, reproduced, published or otherwise used without prior written permission.

No: There is no reasonable causal relationship between the investigational product administered and the AE.

The causal relationship must be provided by the Investigator for all potential trial drugs, i.e. the BI trial drug and for all other trial drugs (such as any active comparator or placebo and for trial procedure).

[figure not shown]
